### **8.2.1      Seriousness Assessment**

When an AE or adverse drug/device reaction occurs, the Investigator responsible for the care of the participant must first assess whether the event is serious using the definition given in [Table 2](#). If the event is classified as 'serious' then the sponsor/designee must be notified within 24 hours as outlined in Section [8.2.6](#).

### **8.2.2      Assessment of Severity**

The Investigator will assess the severity of all AEs and/or adverse drug/device reactions (serious and nonserious) in this study as mild, moderate, or severe.

### **8.2.3      Assessment of Causality**

For all AEs, the relationship of the AE to the administration of the study drug, the surgical procedure, and the devices is to be assessed and captured in the study-specific eCRF.

Relation to study drug is to be assessed according to the definitions in [Table 3](#).

**Table 3: Adverse Event Causality Definitions**

Related	Description	Event Type
NO (unrelated, unlikely to be related)	The time course between the administration of study drug and the occurrence or worsening of the AE rules out a causal relationship or another cause (concomitant drugs, therapies, complications, etc.) is suspected.	Unrelated AE or SAE
YES (possibly, probably, or definitely related)	The time course between the administration of study drug and the occurrence or worsening of the AE is consistent with a causal relationship and no other cause (concomitant drugs, therapies, complications, etc.) is more likely. The definition implies a reasonable possibility of a causal relationship between the event and the study drug. This means that there are facts (evidence) or arguments to suggest a causal relationship.	AR or SAR

AE = adverse event; SAE = serious adverse event; AR= adverse reaction; SAR = serious adverse reaction.

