## 8.2.4 Assessment of Expectedness

### 8.2.4.1 Unexpected Serious Adverse Reaction

If there is at least a reasonable possibility of a causal relationship between the event and the study drug, the Sponsor must assess the expectedness of the event. An unexpected serious adverse reaction (SAR) is one that is not reported in the current IB, or one that is more frequently reported or more severe than previously reported. In view of the limited clinical experience with the study drug, there are at present no events considered as expected. Therefore, any SAE that is assessed as related to study drug (i.e., considered a SAR) will be deemed an unexpected serious adverse reaction) and safety reporting guidelines will apply (Section 8.2.6).

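### Table 3 sets different thresholds for a competing cause in its NO and YES rows, so one adverse event can be both unrelated and related to study drug

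*Combined protocol and SAP*

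**What the plan says.** Section 8.2.3 requires, for all AEs, that "the relationship of the AE to the administration of the study drug, the surgical procedure, and the devices is to be assessed". For the drug it gives a rule: "Relation to study drug is to be assessed according to the definitions in" Table 3.

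Table 3 has two rows.

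- The row labelled "NO (unrelated, unlikely to be related" applies when the time course "rules out a causal relationship or another cause (concomitant drugs, therapies, complications, etc.) is suspected". Its event type is an unrelated AE or serious AE (SAE).
- The row labelled "YES (possibly, probably, or definitely related" applies when the time course is "consistent with a causal relationship and no other cause (concomitant drugs, therapies, complications, etc.) is more likely". Its event type is an adverse reaction or serious adverse reaction (SAR). The cell adds that this definition implies a reasonable possibility of causality, backed by evidence or argument.

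Section 8.2.4.1 uses the same standard for the sponsor's expectedness assessment: "If there is at least a reasonable possibility of a causal relationship between the event and the study drug". It then treats "any SAE that is assessed as related to study drug" as a SAR and as unexpected, which brings Section 8.2.6.4 (expedited reporting) into play.

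The Synopsis (criteria for evaluation, safety) and Section 8 both list relatedness among the AE features to be described. Safety and tolerability are the primary objective.

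**The concern.** A two-way classification needs rows that exclude each other. Here NO turns on whether another cause is suspected at all, while YES turns on whether another cause is more likely than the drug. A cause can be suspected without being more likely, and an event in that position satisfies both descriptions.

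This trial can readily produce such events. Drug, surgery and device are delivered in one session (Section 5.5.3), and the NO text names complications as a possible other cause. Section 1.4.2 lists headache, nausea, confusion and seizures among the risks of catheter placement. The same section reports that in the Phase 2 study headache occurred in 7 AAV-GAD and 2 sham participants, and nausea in 6 and 2. Those figures do not show a drug effect. They only illustrate events for which a procedural cause will be suspected while the drug is not excluded.

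At stake is the consistency of the drug-relatedness rating, both in the safety evaluation and in deciding which SAEs are SARs.

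**Working it through.** The plan gives no figure to reproduce; the check is one of logic.

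**Conditions, from Table 3**

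- NO = (timing rules the drug out) OR (another cause is suspected)
- YES = (timing is consistent) AND (no other cause is more likely)

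The row labels and the reasonable-possibility sentence are treated as explanation, not as further conditions.

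**Step 1: what the complement of YES would be.** Negating YES gives: timing is not consistent, OR another cause is more likely. The printed NO row differs in both parts. On cause it is wider (suspected, instead of more likely). On timing it is narrower (ruled out, instead of not consistent).

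**Step 2: the overlap.** Take consistent timing and a suspected alternative that is no more likely than the drug.

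- NO: false OR true = true.
- YES: true AND true = true.

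The event is an unrelated AE or SAE under one row and an adverse reaction or SAR under the other.

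**Step 3: is there a priority rule?** Section 8.2.3, Table 3 and Section 8.2.4.1 contain none.

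**Step 4: does the result depend on how the states are divided?** The documents define no grid, so the following is an assumption: three timing states by four states of the alternative cause.

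| Timing | None suspected | Suspected, less likely than drug | Suspected, equally likely | More likely than drug |
|---|---|---|---|---|
| Ruled out | NO | NO | NO | NO |
| Neither ruled out nor consistent | neither | NO | NO | NO |
| Consistent | YES | both | both | NO |

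Totals: 2 both + 1 neither + 8 NO only + 1 YES only = 12.

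Range over other divisions:

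| Grid | Cells | Both | Neither |
|---|---|---|---|
| 3 timing × 4 cause | 12 | 2 | 1 |
| 2 timing × 4 cause (no middle timing state) | 8 | 2 | 0 |
| 3 timing × 3 cause (less and equally likely merged) | 9 | 1 | 1 |
| 2 timing × 3 cause | 6 | 1 | 0 |

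The overlap appears in every grid. The gap appears only if a middle timing state is allowed. The cells are categories, not events, so these counts say nothing about frequency.

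**Step 5: test of remedies on the 3 × 4 grid.** YES is met in 3 cells.

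- Changing only the cause clause of NO (suspected to more likely) gives NO in 6 cells. The overlap is 0, but 12 − 6 − 3 = 3 cells fit neither row.
- Making NO the exact complement of YES gives 12 − 3 = 9 NO cells, with 0 both and 0 neither.

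The timing clause therefore has to be aligned together with the cause clause.

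**The case against.** The best answer is that each row should be read as a whole. Beside a label that says unrelated or unlikely, a suspected other cause naturally means one suspected as the explanation. A drug cause at least as likely as its rival is possibly related, which is the YES label. Section 8.2.4.1 uses the same reasonable-possibility standard. Section 8.2.3 also asks for drug, procedure and device relationships, which implies that blaming the procedure does not settle the drug rating. Rater instructions in the electronic case report form, which are not in the documents, may make all this explicit.

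Much of this stands. The documents lean towards YES, and a careful rater would probably land there. But the lean comes from labels and explanatory text that conflict with the NO description and do not limit it. Section 8.2.3 does not say that a suspected procedural cause leaves the drug rating open, while the NO text lists complications among the other causes. A rater who follows that text literally can code as unrelated an event that meets the standard in Section 8.2.4.1.

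The objection also succeeds against the gap. If timing that does not rule the drug out counts as consistent, every event fits at least one row. Section 8.2.5 mentions uncertain causality, but in connection with repeating laboratory tests; it does not define a timing state.

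**Conclusion.** The point holds as a minor defect of wording that is worth correcting. The overlap follows from the current Table 3 text under every division of states tested. It rests on reading the row descriptions as the operative conditions. The gap is secondary and depends on the reading of timing.

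The possible effect is inconsistent or under-coded drug relatedness, and inconsistent SAR status among SAEs. Its size cannot be estimated, because the documents give no breakdown of AEs by competing cause.

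A reader might infer more than the documents support:

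- **Missed expedited reports.** SAR status does lead to expedited reporting, but Section 8.2.6.2 sends every SAE to the sponsor within 24 hours whatever its drug rating. A missed report is not shown.
- **Bias between arms.** Section 5.3 keeps investigators and study staff other than the surgical team, pharmacist and radiologist unaware of assignment. Nothing indicates a direction.
- **A share of events misclassified.** The grid counts are not proportions of events.
- **Damage to the safety tables in general.** Total AE counts and the summaries by system organ class and preferred term (Section 10.1.3.1) do not use the drug rating.

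**What to change.** Keep the YES row and make NO its exact complement, for example: *The time course is not consistent with a causal relationship, or another cause is more likely than study drug.*

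Add a note to Table 3 stating whether timing that cannot be ruled out counts as consistent, in line with the reasonable-possibility standard in Section 8.2.4.1. If it does not count as consistent, the two overlapping cells in the grid become YES, the unplaced cell becomes NO, and no cell that is NO only today moves. If it does, the middle timing row is rated like the consistent row. Two cells that are NO only under the three-state reading then become YES, which is a policy choice and should be made openly.

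Add to Section 8.2.3: *A suspected surgical, device or other cause does not by itself make an event unrelated to study drug.*

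The cost is one table cell, one note and one sentence, with the case report form guidance aligned and drug ratings already made rechecked in a trial of about 14 participants. The downside is that somewhat more AEs may be labelled possibly related.

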## 8.2.4 Assessment of Expectedness

### 8.2.4.1 Unexpected Serious Adverse Reaction

If there is at least a reasonable possibility of a causal relationship between the event and the study drug, the Sponsor must assess the expectedness of the event. An unexpected serious adverse reaction (SAR) is one that is not reported in the current IB, or one that is more frequently reported or more severe than previously reported. In view of the limited clinical experience with the study drug, there are at present no events considered as expected. Therefore, any SAE that is assessed as related to study drug (i.e., considered a SAR) will be deemed an unexpected serious adverse reaction) and safety reporting guidelines will apply (Section 8.2.6).

## 8.2.5 Clinical Laboratory Abnormalities

It is the responsibility of the Investigator to assess the clinical significance of all abnormal laboratory values as defined by the appropriate reference range(s). All abnormal values assessed to be of clinical concern and at least possibly related to study drug or of uncertain causality should be repeated. Clinically significant abnormal laboratory values occurring during the clinical study are to be followed until repeat tests return to normal, stabilize, or are no longer clinically significant.

An abnormal laboratory value that is not already associated with an AE is to be recorded as an AE if intervention for management of the abnormality is required or at the discretion of the Investigator.

## **8.2.6 Safety Reporting Requirements**

All AEs, serious and non-serious, will be fully documented on the appropriate eCRF. For each AE, the Investigator must provide its duration (start and end dates or ongoing), severity, assessment of causality, and whether specific action or therapy was required.

All adverse events and special reporting situations, whether serious or non-serious, will be reported from the time a signed and dated ICF is obtained until the participant's last study visit.

### **8.2.6.1 Investigator Responsibilities Relating to Safety Reporting**

The Investigator will assume overall responsibility for evaluating and reporting AEs. In urgent situations, a member of the study team may report on their behalf, while making every effort to discuss the event with them. All nonserious AEs and ARs, including all events observed following study drug administration, should be recorded in the participant's medical notes, and in the eCRF. Serious Adverse Events and SARs should be reported to the Sponsor or designee immediately once the Investigator becomes aware of the event (in no circumstance should this notification take longer than 24 hours) (see Section [8.2.6.2](#)).

All AEs, which include clinical laboratory test results, that occur after the time of informed consent until the final visit are to be documented. Participants should be instructed to report any AE that they experience to the Investigator, whether or not they think the event is due to study drug. Once written informed consent is obtained, the Investigator should make an assessment for AEs at each visit and record the event on the appropriate AE eCRF.

Wherever possible, a specific disease or syndrome rather than individual associated signs and symptoms should be identified by the Investigator and recorded on the eCRF. However, if an observed or reported sign or symptom is not considered a component of a specific disease or syndrome by the Investigator, it should be recorded as a separate AE on the eCRF. Additionally, the condition that led to a medical or surgical procedure (e.g., surgery, endoscopy, tooth extraction, or transfusion) should be recorded as an AE, not the procedure itself.

Clinically significant abnormal laboratory or other examination findings (e.g., ECG) that are detected during the study or significantly worsen during the study should be reported as AEs. The Investigator is to exercise their medical and scientific judgment in deciding whether an abnormal laboratory finding, or other abnormal assessment is clinically significant. Clinically significant abnormal laboratory values occurring during the clinical study are to be followed until repeat tests return to normal, stabilize, or are no longer clinically significant.

### **8.2.6.2 Serious Adverse Event Reporting – Procedures for Investigators**

All adverse events are to be recorded in the participant's medical notes and the CRF from the date of written informed consent until the last study visit. The Sponsor or designee must be notified of all SAEs within 24 hours of the Investigator becoming aware of the event during this period. The Investigator will respond to any SAE queries raised by the Sponsor or designee as soon as possible.

After the last visit, any SAE reported to the Investigator and considered causally related to study treatment should be reported as part of the follow-up study.

The SAE form must be completed by the Investigator (i.e., the individual named on the delegation of responsibilities list who is responsible for the participant's care) with attention paid to the severity, and causality of the event. In the absence of the Investigator, the SAE form should be completed and signed by a member of the site study team and emailed as appropriate within the required timeframe. The Investigator should check the SAE form at the earliest opportunity, make any changes necessary, sign and then email to the Sponsor or designee (see Section 8.2.8). Systems will be in place at the site to enable the Investigator to check the form for clinical accuracy as soon as possible.

The minimum components required for reporting a SAE are the patient ID and year of birth, name of reporting Investigator and sufficient information on the event to confirm seriousness. Any further information regarding the event that is unavailable at the time of the first report should be sent as soon as it becomes available.

For information on code-breaking and unblinding in the event of medical emergencies, please refer to Section 5.4.

Participants must be followed up until clinical recovery is complete and laboratory results have returned to normal or baseline values, or until the event has stabilized. Follow-up should continue after completion of the study if necessary. Follow-up SAE forms (clearly marked as follow-up) should be completed and emailed to the Sponsor or designee (see Section 8.2.8) as further information becomes available. Additional information and/or copies of test results, etc. may be provided separately. The participant's name and full date of birth must not be used in any correspondence and must be blacked out and replaced with study identifiers on any test results, should they be provided.

### 8.2.6.3 Pregnancy Reporting

If a participant becomes pregnant prior to receiving treatment, the participant should not receive treatment and will be replaced. If a participant becomes pregnant after receiving treatment, the participant will continue the protocol-defined assessments. However, any assessment that in the opinion of the Investigator or primary physician would be deemed a risk to the pregnancy may be omitted or deferred.

In case a pregnancy occurs after study treatment is administered, the participant's general practitioner is to be notified that she is participating in a gene therapy study and that, although the risks involved are minimal, there is a chance of gene transfer to the unborn child.

A pregnancy is not considered to be an AE or SAE; however, it must be reported to the Sponsor or designee using a pregnancy report form, within 24 hours of the Investigator becoming aware of the event.

If the female partner of a male participant becomes pregnant while the participant is receiving study drug or within the safety follow-up period defined in the protocol, the Investigator should notify the Sponsor or designee as described above.

After written informed consent is obtained from the female partner (via a pregnant partner consent form), the pregnancy should be followed until its outcome is known. Once the outcome of the pregnancy is known, the pregnancy report form should be completed and faxed/mailed to the Sponsor or designee (see Section 8.2.8). If the outcome of the pregnancy meets the criteria for immediate classification as an SAE (i.e., postpartum complication, spontaneous abortion, stillbirth, neonatal death, or congenital anomaly), the Investigator should follow the procedures for reporting an SAE.

#### **8.2.6.4 Expedited Reporting**

The Sponsor or designee will report all relevant information about serious and unexpected adverse reactions that are fatal or life-threatening as soon as possible to the relevant Competent Authorities, and, in any case, no later than 7 days after knowledge by the Sponsor or designee of such a case. Relevant follow-up information is to be communicated within an additional 8 days.

All other serious and unexpected adverse reactions will be reported to the relevant Competent Authorities as soon as possible but within a maximum of 15 days of first knowledge by the Sponsor or designee.

The Sponsor or designee also will inform all Investigators of the SAE/SAR as required per local regulation.

#### **8.2.7 Special Situation Reports**

Special situation reports include reports of study treatment error and reports of adverse reactions associated with product complaints.

- **Study treatment error:** Is any unintentional error in the prescribing, dispensing, or administration of a medicinal product by a healthcare professional, participant, or consumer, respectively. The administration or consumption of the unassigned treatment, higher doses than planned and administration of an expired product are always reportable as study treatment errors.
- **Product complaint:** Is defined as any written, electronic, or oral communication that alleges deficiencies related to the identity, quality, durability, reliability, safety, effectiveness, or performance of a drug or device after it is released for distribution. A special situations report will only be completed if a complaint is associated with an adverse drug reaction. For more information, please refer to the Pharmacy Manual.

All special situation events as described above must be reported in the same time frame as SAEs (see Section 8.2.6.2). All AEs associated with these special situation reports should be reported as

AEs or SAEs as well as recorded on the AE eCRF and/or the SAE report form. Details of the symptoms and signs, clinical management, and outcome should be provided, when available.

## **8.3 PHYSICAL AND NEUROLOGICAL EXAMINATIONS**

A standard/limited physical examination and neurological examination will be performed.

## **8.4 CLINICAL SAFETY LABORATORY EVALUATIONS**

The actual dates and times of sample collection must be recorded in the eCRF or laboratory requisition form.

Refer to the SoA ([Table 1](#)) for the timing and frequency of all sample collections.

Blood samples for hematology, chemistry, and coagulation panels and urine samples will be obtained for the tests outlined in [Table 4](#), and testing will be performed at the participating institution.

Note that a serum pregnancy test must be performed for women of childbearing potential at Screening and within 1 week prior to the surgery.

Coronavirus Disease 2019 (COVID-19) testing and follow-up will be done as per institution protocol.

Screening results will be assessed by the Investigator for inclusion of participants in the study. Additionally, unscheduled clinical laboratory tests may be obtained at any time during the study at the Investigator's discretion. The diagnosis corresponding to any clinically significant abnormality or abnormality requiring treatment/intervention must be recorded as an AE.

**Table 4: Clinical and Safety Related Laboratory Tests**

Standard Safety Chemistry Panel	
Alanine aminotransferase	Albumin
Alkaline phosphatase	Aspartate aminotransferase
Blood urea nitrogen	Calcium
Chloride	Glucose
Creatinine	Inorganic phosphorus
Lactate dehydrogenase	Magnesium
Potassium	Sodium
Total and direct bilirubin	Total carbon dioxide
Total protein	Uric acid

Hematology	
Hematocrit	Hemoglobin
Mean corpuscular volume	Platelets
White blood cell count and differential [1]	
Coagulation	
Partial thromboplastin time	International normalized ratio
Prothrombin time	
Urinalysis	
Bilirubin	Glucose
Hemoglobin	Ketones
Microscopy [2]	pH
Protein	Specific gravity

1. Manual microscopic review is performed only if white blood cell count and/or differential values are out of reference range.
2. Microscopy is performed only as needed based on positive dipstick test results.

